7.2. Data Listings to be Generated

- -Listing 16.1.1.1: Subject Disposition All Subjects Screened
- Listing 16.1.1.2: Eligibility All Subjects
- Listing 16.1.1.3: Major Protocol Deviations All Subjects Randomized

Listing 16.1.1.4: Subjects Excluded from the Efficacy Analysis – All Subject Randomized

Cytel

Statistical Analysis Plan

Sponsor:	Ocular Therapeutix, Inc.		
Protocol:	CLN-Protocol-0054		
Document Version No.:	V1.0	Document Date:	01-OCT-2021

Listing 16.1.2: Demographic and Baseline Characteristics - mITT and Cohort 1

- Listing 16.1.3.1: Ocular Medical History mITT and Cohort 1
- Listing 16.1.3.2: Non-Ocular Medical History mITT and Cohort 1
- Listing 16.1.4: Treatment Exposure SAFETY
- Listing 16.1.5: Schirmer's Test without Anesthesia Result- mITT and Cohort 1
- Listing 16.1.6: CFS Assessment mITT and Cohort 1
- Listing 16.1.7: CLGS Assessment mITT and Cohort 1
- Listing 16.1.8: VAS of Eye Dryness Score mITT and Cohort 1
- Listing 16.1.9: Ocular Surface Disease Index questionnaire (OSDI©) mITT and Cohort 1
- Listing 16.1.10: Standardized Patient Evaluation of Eye Dryness (SPEED) mITT and Cohort 1
- Listing 16.1.11: Tear Film Break Up Time (TBUT) mITT and Cohort 1
- Listing 16.1.12: Insert Placement at Visit 2 or Visit 2B mITT and Cohort 1
- Listing 16.1.13: Ease of insertion at Visit 2 or Visit 2B as assessed by the Investigator mITT and Cohort 1
- Listing 16.1.14: Presence of OTX-CSI or HV by Visual Assessment mITT and Cohort 1
- Listing 16.1.15: Ease of visualization as assessed by the Investigator mITT and Cohort 1
- Listing 16.1.16.1: All Adverse Events SAFETY
- Listing 16.1.16.2: Serious Adverse Events SAFETY
- Listing 16.1.16.3: Adverse Events leading to Discontinuation of Treatment SAFETY
- Listing 16.1.16.4: Subject Deaths SAFETY
- Listing 16.1.17: Best Corrected Visual Acuity (BCVA) SAFETY
- Listing 16.1.18: Slit-lamp Biomicroscopy and External Eye Exam SAFETY
- Listing 16.1.19: Intraocular Pressure (IOP) Measurement SAFETY
- Listing 16.1.20: Fundus Examination SAFETY

Listing 16.1.21: Use of Artificial Tears - SAFETY

Cytel

Statistical Analysis Plan

Sponsor:	Ocular Therapeutix, Inc.		
Protocol:	CLN-Protocol-0054		
Document Version No.:	V1.0 Document Date: 01-OCT-2021		

Listing 16.1.22: Urine Pregnancy Test - SAFETY

Listing 16.1.23: Concomitant Medications - SAFETY

Listing 16.1.24: Prior Medications - SAFETY

Sponsor:	Ocular Therapeutix, Inc.		
Protocol:	CLN-Protocol-0054		
Document Version No.:	V1.0 Document Date: 01-OCT-2021		

7.3. SAS Codes

7.3.1. variables used in SAS codes:

TRPG1N	Treatment groups with 4 groups
TRPG1N_FG1	Dummy variables based on TRPG1N
TRPG1N_FG2	
TRPG1N_FG3	
AVAL2	Value at visit 2
AVAL4	Value at visit 3
AVAL5	Value at visit 4
AVAL6	Value at visit 5
AVAL7	Value at visit 6
AVAL8	Value at visit 7
СНБ	Change from baseline
CRIT4	Categorical Schirmer test (>=10 mm vs <10 mm) at visit 3
CRIT5	Categorical Schirmer test at visit 4
CRIT6	Categorical Schirmer test at visit 5
CRIT7	Categorical Schirmer test at visit 6
CRIT8	Categorical Schirmer test at visit 7
CRIT9	Categorical Schirmer test at visit 8
SEFN	Study eye flag

Sponsor:	Ocular Therapeutix, Inc.		
Protocol:	CLN-Protocol-0054		
Document Version No.:	V1.0	Document Date:	01-OCT-2021

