2.6.1.2. Secondary Efficacy Variables

- 1- Percent of eyes with ≥10 mm Increase in Schirmer Test from Baseline at Week 12
- 2- Eye Dryness Severity and Frequency Scores (VAS) and their CFB to each post-baseline visit.
- 3- Schirmer Test (mm) and its change from baseline (CFB) to each post-baseline visit.
- 4- Total Corneal Fluorescein Staining (tCFS) using National Eye Institute (NEI) scale and its CFB to each post-baseline visit.
- 5- CFS sub-regions using NEI scale and its CFB to each post-baseline visit.
- 6- Conjunctival Lissamine Green Staining using NEI scale and its CFB to each post-baseline visit.
- 7- Ocular Surface Disease Index questionnaire (OSDI©) (total score, each of the three domains and the individual questions) and its CFB to each post-baseline visit.
 - OSDI total score will be calculated using below OSDI© formula:

$$Overall \ OSDI \ score \ = \frac{(Sum \ of \ scores \ for \ all \ questions \ answered) \ \times \ 25}{number \ of \ questions \ answered}$$

OSDI score for each section (ABC) will be calculated using below formula:

OSDI score for each section (A, B, C)

```
=\frac{(Sum of scores for all questions answered for the section) \times 25}{number of questions answered in that section}
```

The OSDI is scored on a scale of 0 to 100, with higher scores representing greater disability.

- 8- SPEED measures (overall score and individual questions) and its CFB to each postbaseline visit.
 - SPEED overall score will be calculated as Sum of the questions in frequency and severity of symptoms.

Sponsor:	Ocular Therapeutix, Inc.			
Protocol:	CLN-Protocol-0054			
Document Version No.:	V1.0 Document Date: 01-OCT-2021			

The final score ranges from 0 to 28, with higher scores representing the severe dryness.

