4.7.3. Secondary Analyses

1. To analyze the efficacy endpoint of percent of eyes with ≥10 mm Increase in Schirmer Test from Baseline at Visit 7 (Week 12) and other Post-Baseline Visits, the logistic regression or Fisher's exact test will be used as described below:

The two groups of Schirmer test (≥10 mm vs <10 mm) will be compared between treatment groups as CSI Formulation 1 to HV Formulation 2B, CSI Formulation 2A to HV Formulation 2B, CSI Formulation 1 to HV Formulation 3, CSI Formulation 2A to HV Formulation 3, will be reported. This model will also be used to compare overall OTX-CSI (combined Formulation 1 and Formulation 2A) to each HV Formulation (2B and 3) using the logistic regression.

The above analyses will be performed on the change from baseline in Schirmer test (\geq 10 mm vs <10 mm) derived based on the imputed Schirmer data using FCS MI (details in section 4.2.9.1) at visit 7 on the mITT and PP populations using the logistic regression and Odds Ratio (OR), 95% confidence interval for OR, and P-value for OR will be reported. In addition, sensitivity analyses will be done using LOCF and observed data and the two groups of Schirmer test (\geq 10 mm vs <10 mm) will be compared between treatment groups using the Fisher's exact test on this endpoint. These analyses will also be performed on all post-baseline visits.

2. To analyze the efficacy endpoints of Eye Dryness Severity and Eye Dryness Frequency, statistical modeling similar to the primary efficacy endpoint analysis (4.7.1) will be performed for each post-baseline visit (Visit 3, Visit 4, Visit 5, Visit 6, Visit 7, and Visit 8)

Sponsor:	Ocular Therapeutix, Inc.		
Protocol:	CLN-Protocol-0054		
Document Version No.:	V1.0 Document Date: 01-OCT-2021		

using the MCMC MI imputed data on the mITT and PP populations. In addition, sensitivity analyses done for the primary efficacy endpoint will also be performed on this endpoint.

3. To analyze the efficacy endpoints of total Corneal Fluorescein Staining (tCFS) and its sub-region, statistical modeling similar to the primary efficacy endpoint analysis (4.7.1) will be performed for each post-baseline visit (Visit 3, Visit 4, Visit 5, Visit 6, Visit 7, and Visit 8) using the MCMC MI imputed data on the mITT and PP populations. In addition, sensitivity analyses done for the primary efficacy endpoint will also be performed on this endpoint.

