5. CHANGES TO PLANNED ANALYSES

The language in the SAP will supersede the language in the protocol should there be a discrepancy.

The primary analysis will be repeated for all visits using observed data (without imputation) for both mITT and PP populations. These results will be provided in sensitivity analyses section.

The difference between two OTX-CSI hydrogel formulations as well as the difference between two HV formulations will not be studied. HV formulations will not be combined.

Wilcoxon rank sum test will be used only to analyze LOCF and observed data.

For Eye Dryness Severity and Eye Dryness Frequency, as well total Corneal Fluorescein Staining (tCFS) and its sub-region the main analysis will be based on MCMC MI and sensitivity analyses will be done using LOCF, observed data, and FCS.

For the first secondary efficacy endpoint analysis, for the main analysis, the two groups of change from baseline in Schirmer test (\geq 10 mm vs <10 mm) at visit 7 will be compared between treatment groups using the logistic regression and for the sensitivity analyses, the groups will be compared using LOCF and observed data by Fisher's exact test; Clopper-Pearson method will be used to calculate 95% confidence interval of the proportion of subject with change from baseline in Schirmer Test \geq 10 mm; to calculate 95% confidence interval of the proportion difference, the Chan and Zhang (1999) method will be used.

These analyses will also be performed on all post-baseline visits.

Sponsor:	Ocular Therapeutix, Inc.		
Protocol:	CLN-Protocol-0054		
Document Version No.:	V1.0 Document Date: 01-OCT		01-OCT-2021

6. **REFERENCES**

American Academy of Ophthalmology Cornea/External Disease Panel. Preferred Practice Pattern[®] Guidelines. Dry Eye Syndrome. San Francisco, CA: American Academy of Ophthalmology; 2018. Available at www.aao.org/ppp. Accessed September 23, 2019.

- Disease in the United States Among Adults Aged 18 Years and Older. Am J Ophthalmol. Oct;182:90-98.
- Perry HD. Dry eye disease: Pathophysiology, classification, and diagnosis. Am J Manag Care. 2008;14:S79-S87.
- Schultz C. Safety and efficacy of cyclosporine in the treatment of chronic dry eye. Ophthalmol Eye Dis. 2014;6:37-42.

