7.3.3. SAS codes to impute the missing using FCS MI

```
PROC MI DATA=pr1t SEED=918411 OUT=pr1fcsy MINIMUM=0 MAXIMUM=35 ROUND=0.1
NIMPUTE=25;
where SEFL="Y";
class TRPG1N CRIT4 CRIT5 CRIT6 CRIT7 CRIT8 CRIT9;
VAR TRPG1N AVAL2 AVAL4 AVAL5 AVAL6 AVAL7 AVAL8 AVAL9;
/*This part imputes the continues Schirmer test */
fcs nbiter=200 reg (AVAL2=TRPG1N );
fcs nbiter=200 reg (AVAL4=TRPG1N AVAL2);
fcs nbiter=200 reg (AVAL5=TRPG1N AVAL2 AVAL4);
fcs nbiter=200 reg (AVAL5=TRPG1N AVAL2 AVAL4);
fcs nbiter=200 reg (AVAL6=TRPG1N AVAL2 AVAL4 AVAL5);
fcs nbiter=200 reg (AVAL6=TRPG1N AVAL2 AVAL4 AVAL5);
fcs nbiter=200 reg (AVAL8=TRPG1N AVAL2 AVAL4 AVAL5 AVAL6);
fcs nbiter=200 reg (AVAL8=TRPG1N AVAL2 AVAL4 AVAL5 AVAL6 AVAL7);
fcs nbiter=200 reg (AVAL9=TRPG1N AVAL2 AVAL4 AVAL5 AVAL6 AVAL7 AVAL8);
RUN;
```

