7.3.6. SAS codes to generate and pool proportions using MI data

```
proc surveyfreq data= pr1fcsy;
            by avisitn imput;
            tables TRPG1*CRIT8 / row ;
            ods output CrossTabs=mi_perc_out;
```

run;

```
proc mianalyze data=mi_perc_out;
    by TRPG1 CRIT8;
    modeleffects RowPercent;
    stderr RowStdErr;
    ods output ParameterEstimates=pooled_percent;
run; quit;
```

7.3.7. SAS codes to generate and pool the Odds Ratio (OR) using MI data

```
ods output ParameterEstimates =OR_out;

proc surveylogistic data= pr1fcsy;

by avisitn imput;

class TRPG1 / param = ref;

model CRIT8 (desc) =TRPG1;

where TRPG1N in (1 3);

run;

proc mianalyze data=OR_out;
```

```
modeleffects Estimate ;
stderr StdErr;
ods output ParameterEstimates=pooled_OR;
```

run; quit;

Sponsor:	Ocular Therapeutix, Inc.			
Protocol:	CLN-Protocol-0054			
Document Version No.:	V1.0	Document Date:	01-OCT-2021	

7.3.8. SAS codes to output 95% CI for proportions using Clopper-Pearson method and 95% CI for the proportion difference using Chan and Zhang (1999) method using observed and LOCF data

ods output RiskDiffCol1=RiskDiffCol1 FishersExact=FishersExact;
proc freq data=adoe;

table TRPG1N* CRIT8 / fisher;

exact riskdiff(method=score);

run;

7.3.9. SAS codes to designate study eye randomly in a case both eyes have the same total corneal fluorescein staining score

- 1- Create a SAS dataset RND1 with 1000 observations,
- 2- Create a variable named FOCID. The first 500 observation with value of "OD" (Right Eye) the last
- 500 observation with value of "OS" (Left Eye)
- 3- Generate a random number using RANUNI (Uniform distribution)
- 4- Sort this dataset by random variable ****;

data rnd1;

```
do i=1 to 500;
FOCID="OD";
rand=ranuni(54603);
output;
end;
do i=501 to 1000;
FOCID="OS";
rand=ranuni(54603);
output;
end;
run;
proc sort data=rnd1(drop=i); by rand; run;
data rnd1; set rnd1; VSORT= n ; run;
proc sort data=rnd1; by VSORT; run;
****
5- Sort the subject by using 2 variables
```

```
a- date of randomization for randomized subjects / date of informed consent for open label subjects
```

- b- random number
- c- subject number

Sponsor:	Ocular Therapeutix, Inc.			
Protocol:	CLN-Protocol-0054			
Document Version No.:	V1.0	Document Date:	01-OCT-2021	

6- Then merge this dataset with RND1 and then selected FOCID will be their study eye.****; proc sort data=idsd.suppdm out=dm1(keep=USUBJID QVAL);

where QNAM="RANDNUMB";

by USUBJID;

run;

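### As printed, the SAP code for the 10 mm Schirmer responder endpoint sets the flag before imputation, and 7.3.7 and 7.3.8 appear to report opposite categories of it

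*SAP*

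**What the plan says.** The SAP text is consistent on the endpoint. Section 2.6.1.2 lists first, among the secondary variables, the percentage of eyes with a 10 mm or greater "Increase in Schirmer Test from Baseline at Week 12". Section 5 restates it as a comparison of "the two groups of change from baseline in Schirmer test". Section 4.7.3 says that for the main analysis the two-level outcome is "derived based on the imputed Schirmer data using FCS MI", analysed by logistic regression. LOCF and observed data are sensitivity analyses, using Fisher's exact test. Section 5 adds Clopper-Pearson intervals for the proportion and Chan-Zhang intervals for the difference.

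The code appendix reads as follows.

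- 7.3.1 labels CRIT4 "Categorical Schirmer test (>=10 mm vs <10 mm) at visit 3". The Week 12 flag, CRIT8, is labelled only "Categorical Schirmer test at visit 7". Neither label mentions change from baseline, and no coding is given.
- 7.3.3 (FCS step, input `pr1t`, output `pr1fcsy`) has the statement "class TRPG1N CRIT4 CRIT5 CRIT6 CRIT7 CRIT8 CRIT9". Its VAR list and regressions name only treatment and the AVAL variables.
- 7.3.6 (proportions) and 7.3.7 (odds ratio) both read `pr1fcsy`. The model in 7.3.7 is "model CRIT8 (desc) =TRPG1".
- 7.3.8 (Fisher's test and exact intervals, observed and LOCF data) reads `adoe` and keeps "ods output RiskDiffCol1=RiskDiffCol1 FishersExact=FishersExact".

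**The concern.** The code appendix is what a programmer will follow, and here it departs from the text in two ways that matter and one that is minor.

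- **Timing.** A flag that already exists when imputation starts, and is not itself imputed, cannot reflect the imputed Schirmer values. The tables titled as FCS multiple imputation (14.2.3.1.1 to 14.2.3.1.4) would then hold an observed-case analysis. The observed-data sensitivity analysis would use the same eyes with the same flags, so agreement between the two would say nothing about missing data.
- **Direction.** One program takes the last level of CRIT8 as the event and the other reports the first. If so, the odds ratio and the intervals for the same endpoint describe opposite outcomes. SAP 4.2.1 fixes differences as OTX-CSI minus HV, so a benefit could be tabulated with the sign of a harm, or an odds ratio inverted.
- **Label (minor).** The wording in 7.3.1 leaves out that the 10 mm applies to a change.

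**Working it through.** The documents give no responder rate, dropout rate or sample size calculation, so there is no stated figure to reproduce. The check traces the code; the numbers below are illustrations on assumed values.

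**1. Timing of the flag**

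- 4.7.3 requires: impute the continuous Schirmer values, then derive the flag.
- Variables named in CLASS in 7.3.3 must be in the input, so CRIT4 to CRIT9 exist in `pr1t` before imputation.
- The VAR list is TRPG1N, AVAL2 and AVAL4 to AVAL9. No CRIT variable is imputed; PROC MI passes the flags through unchanged.
- 7.3.6 and 7.3.7 take CRIT8 from `pr1fcsy`. No derivation is printed in between.

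Run as printed, an eye without a Week 12 value has AVAL8 filled in and CRIT8 still missing, in all 25 copies.

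Eyes used in an arm of n with assumed missing fraction d: n × (1 − d).

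| d | Arm of 40 | Arm of 20 |
|---|---|---|
| 5% | 38 | 19 |
| 10% | 36 | 18 |
| 15% | 34 | 17 |
| 20% | 32 | 16 |

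The pooled variance is T = W + (1 + 1/25) × B, where W is the within-imputation and B the between-imputation variance. A flag identical in all 25 copies gives B = 0, so T = W. In one simulated arm of 40 with 6 eyes missing (baseline 1 to 10 mm, mean change 3 mm, SD 6 mm, all assumed), the pre-set flag used 34 eyes with B = 0. The flag re-derived after imputation used all 40, with B about 0.0002.

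**2. Direction of the flag**

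With default ordering, the descending option makes the last sorted level the event, and column 1 of the frequency table is the first sorted level. For a two-level variable these are always different categories:

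| Coding of CRIT8 | 7.3.8, column 1 | 7.3.7, event |
|---|---|---|
| 0 = no, 1 = yes | non-responder | responder |
| N / Y | non-responder | responder |
| '<10' / '>=10' | non-responder | responder |
| 1 = yes, 2 = no | responder | non-responder |

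Assume responder rates of 25% (OTX-CSI) and 10% (HV):

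- Responders: difference 0.25 − 0.10 = +0.15; odds ratio (0.25/0.75) / (0.10/0.90) = 3.00.
- Non-responders: difference 0.75 − 0.90 = −0.15; odds ratio 1/3.00 = 0.33.
- With 0/1 coding, the programs give odds ratio 3.00 beside difference −0.15. With 1 = responder and 2 = non-responder, they give 0.33 beside +0.15.
- At 20% and 10%, the same steps give responder values of 2.25 and +0.10, and non-responder values of 0.44 and −0.10.

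7.3.6 tabulates and pools both levels of CRIT8, so it has no direction problem.

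**3. Label**

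The 7.3.1 wording could describe a level. Sections 2.6.1.2, 4.7.3 and 5 all state a change or increase from baseline, and they govern. No size is attached to this part.

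**The case against.** The strongest reply is that Section 7.3 prints excerpts, not a complete program. 7.3.6 and 7.3.7 run by `avisitn` and `imput`, which the printed PROC MI step does not create. The primary analysis in 7.3.4 and 7.3.5 reads a dataset `pr2`, containing the change from baseline, whose creation is also not shown. 7.3.8 has no statement restricting it to two groups, though a difference needs two. So unprinted steps exist, one of them may re-derive CRIT8, and 4.7.3 says that this should happen. That stands: a reader might conclude that the imputed responder analysis is certainly an observed-case one, and the documents do not support that much. They do show that the flag is named in the imputation step, that the analysis programs read that step's own output dataset, and that no derivation is written down.

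On direction, a format that reverses the level order, or different coding in `pr1fcsy` and `adoe`, could bring the two programs into line. 7.3.8 serves only the observed and LOCF analyses. Fisher's p-value is the same whichever column is kept, and intervals for non-responders are the exact complement of those for responders. All of this stands. It limits the harm to the reported proportion, interval limits and sign, or to an inverted odds ratio, but the coding that would settle the matter is stated nowhere.

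On the label, a reader might infer that the flag is computed on the Week 12 level, so that an eye entering at 10 mm (allowed by Protocol 7.1) and unchanged would count as a responder. The documents do not support that reading. Section 4.7.3 uses the same shorthand under an item naming the increase from baseline, and then restates it as a change. Only CRIT4 carries the cut point at all.

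**Conclusion.** The concern holds for the code as printed. Unless an unprinted step re-derives CRIT8 after imputation, eyes missing Week 12 are left out of the FCS MI responder result: 6 of 40 in a full arm at an assumed 15% missing, 2 to 8 of 40 over 5% to 20%. If default level ordering and the same unformatted coding apply in both datasets, either the odds ratio or the observed and LOCF proportions and differences describe non-responders, with the sign of the difference or the direction of the odds ratio reversed. The label is a drafting gap only.

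This is a secondary endpoint. The primary analysis of Schirmer change does not use CRIT8 and is not affected. It should be corrected because it touches the first-listed secondary endpoint and the correction is cheap. Confidence is medium, since the intermediate steps and the coding are not printed.

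**What to change.** In the SAP code appendix:

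1. Remove CRIT4 to CRIT9 from the CLASS statement in 7.3.3.
2. After 7.3.3, print a step that derives in each of the 25 imputed datasets: CRITn = 1 if AVALn minus baseline is at least 10 mm, else 0. Run 7.3.6 and 7.3.7 on that dataset, under a new name.
3. Relabel CRIT4 to CRIT9 in 7.3.1 as an increase from baseline of at least 10 mm, and state the coding.
4. Name the responder level explicitly: an event= option in 7.3.7 and the matching risk-difference column in 7.3.8. Simply switching 7.3.8 to column 2 is not enough, because under 1 = responder, 2 = non-responder that column would be the non-responders.

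The cost is a few lines of code. If a working program already derives the flag after imputation and handles the coding, only the appendix needs correcting. If not, the responder tables (14.2.3.1.1 to 14.2.3.3.4) need programming to the corrected code. The endpoint, the data collected and the care of subjects do not change.

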7.3.2. SAS codes to impute the missing using MCMC MI

PROC MI DATA=pr1t SEED=738493 OUT=pr1mcmcmiy MINIMUM=0 MAXIMUM=35 ROUND=0.1 NIMPUTE=25;

/*The imputation will be done in eye level, SEFL is study eye flag*/

```
where SEFL="Y";

MCMC INITIAL=EM;

VAR TRPG1N_FG1 TRPG1N_FG2 TRPG1N_FG3 AVAL2 AVAL4 AVAL5 AVAL6 AVAL7 AVAL8

AVAL9;
```

RUN;

7.3.3. SAS codes to impute the missing using FCS MI

```
PROC MI DATA=pr1t SEED=918411 OUT=pr1fcsy MINIMUM=0 MAXIMUM=35 ROUND=0.1
NIMPUTE=25;
where SEFL="Y";
class TRPG1N CRIT4 CRIT5 CRIT6 CRIT7 CRIT8 CRIT9;
VAR TRPG1N AVAL2 AVAL4 AVAL5 AVAL6 AVAL7 AVAL8 AVAL9;
/*This part imputes the continues Schirmer test */
fcs nbiter=200 reg (AVAL2=TRPG1N );
fcs nbiter=200 reg (AVAL4=TRPG1N AVAL2);
fcs nbiter=200 reg (AVAL5=TRPG1N AVAL2 AVAL4);
fcs nbiter=200 reg (AVAL5=TRPG1N AVAL2 AVAL4);
fcs nbiter=200 reg (AVAL6=TRPG1N AVAL2 AVAL4 AVAL5);
fcs nbiter=200 reg (AVAL6=TRPG1N AVAL2 AVAL4 AVAL5);
fcs nbiter=200 reg (AVAL8=TRPG1N AVAL2 AVAL4 AVAL5 AVAL6);
fcs nbiter=200 reg (AVAL8=TRPG1N AVAL2 AVAL4 AVAL5 AVAL6 AVAL7);
fcs nbiter=200 reg (AVAL9=TRPG1N AVAL2 AVAL4 AVAL5 AVAL6 AVAL7 AVAL8);
RUN;
```

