4.2.9.1. Imputation Method for Efficacy Endpoints

To impute missing, Markov Chain Monte Carlo (MCMC) multiple imputation (MI), Fully Conditional Specification multiple imputation (FCS MI) and last observation carried forward (LOCF) methods will be used.

For MI, we will have below phases:

1. Imputation Phase: in this phase, the missing data will be imputed using SAS PROC MI and a complete data set will be created. This process of imputation will be repeated 25 times. Therefore, 25 compete datasets will be created. In this phase, treatment group, baseline value, and post-baseline visits from visit 3 to visit 8, respectively, will be included in multiple imputation model.

2. Analysis Phase: each of the 25 complete data sets will be analyzed independently using desired statistical method (e.g. ANCOVA for primary efficacy analysis).

3. Pooling Phase: in this phase the estimates obtained from each analyzed complete dataset from phase 2, will be combined using PROC MIANALYZE.

The analysis of efficacy variables Schirmer Test, Eye Dryness Severity Score and Eye Dryness Frequency Score on mITT and PP populations will be performed by imputing missing data using MCMC MI methodology with repeated 25 times of imputation under the assumption of missingness at random. Last observation carried forward (LOCF) method and Fully Conditional Specification multiple imputation (FCS MI) with 200 burn-in iterations and 25 times of imputation under the assumption of missingness at random will be used for sensitivity analyses (Section 4.7.2). LOCF method will be used for sensitivity analyses.

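### The FCS imputation code behind the main Week 12 responder analysis uses only earlier visits, prints no Visit 6 model, and does not match SAP 4.2.9.1 or the MCMC model

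*SAP*

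**What the plan says.** SAP 4.2.9.1 describes one imputation phase for both multiple-imputation methods: "treatment group, baseline value, and post-baseline visits from visit 3 to visit 8, respectively, will be included in multiple imputation model". It uses MCMC for the main analysis of Schirmer and the two eye dryness scores, and names FCS (200 burn-in iterations, 25 imputations) for sensitivity analyses. Protocol 11.6 likewise assigns MCMC to the primary analyses of efficacy data.

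The MCMC code in SAP 7.3.2 puts treatment and all visits in one joint model: "VAR TRPG1N_FG1 TRPG1N_FG2 TRPG1N_FG3 AVAL2 AVAL4 AVAL5 AVAL6 AVAL7 AVAL8", with `AVAL9` on the next line.

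The FCS code in SAP 7.3.3 has a matching variable list, "VAR TRPG1N AVAL2 AVAL4 AVAL5 AVAL6 AVAL7 AVAL8 AVAL9", but then gives each target its own formula. Week 2 is "fcs nbiter=200 reg (AVAL4=TRPG1N AVAL2" and Week 12 is "fcs nbiter=200 reg (AVAL8=TRPG1N AVAL2 AVAL4 AVAL5 AVAL6 AVAL7". A second line for the same Week 12 target reads "fcs nbiter=200 reg (AVAL8=TRPG1N AVAL2 AVAL4 AVAL5 AVAL6".

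SAP 4.7.3 bases the responder analysis on change from baseline "derived based on the imputed Schirmer data using FCS MI (details in section 4.2.9.1) at visit 7 on the mITT and PP populations", using logistic regression. SAP 5 calls the logistic regression the main analysis, and the code in 7.3.6 and 7.3.7 reads `pr1fcsy`, the FCS output.

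**The concern.** Regressions restricted to the past amount to sequential imputation. That suits monotone dropout, where nothing is observed after the first missing visit. If a subject misses Week 12 but attends Week 16, the later value is informative and this code does not use it. The MCMC model does.

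Three things are at stake.

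- The continuous Week 12 Schirmer endpoint and its responder version impute the same missing values from different conditioning sets.
- The FCS sensitivity analysis of the primary endpoint (SAP 4.7.2) cannot isolate the choice of algorithm, because the predictor set changes as well.
- Text and code do not define one analysis for a main secondary endpoint, and Visit 6 has no stated model.

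**Working it through.** **Reading the code.** SAP 7.3.1 defines `AVAL2` as Visit 2 and `AVAL4` to `AVAL8` as Visits 3 to 7. `AVAL9` is not defined; I read it as Visit 8 from the numbering (`CRIT9` is Visit 8). The nine printed FCS lines are:

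| Target | Visit | Lines printed | Later visits used |
|---|---|---|---|
| AVAL2 | 2 | 1 | none |
| AVAL4 | 3 | 1 | none |
| AVAL5 | 4 | 2, identical | none |
| AVAL6 | 5 | 2, identical | none |
| AVAL7 | 6 | 0 | no model printed |
| AVAL8 | 7 (Week 12) | 2, with and without AVAL7 | none |
| AVAL9 | 8 (Week 16) | 1 | none exist |

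The shorter `AVAL8` line has the predictors one would expect for `AVAL7`. The 25 imputations and 200 iterations in the code agree with the text. The plan states no figure on this point to reproduce.

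**Information lost at Week 12.** The documents give no between-visit correlations, so these are assumptions. Take Week 12 missing, with Visits 2 to 6 and Visit 8 observed.

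*Compound symmetry, correlation r, k predictors.* Residual variance = (1−r)(1+kr)/(1+(k−1)r). The code has k = 5; adding Visit 8 gives k = 6.
- r = 0.3: 0.795 v 0.784, cut 1.4%
- r = 0.5: 0.583 v 0.571, cut 2.0%
- r = 0.8: 0.238 v 0.232, cut 2.6%

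*AR(1), correlation r per 3 weeks.* Week 9 to 12 is 3 weeks and Week 12 to 16 is 4 weeks. Put a = r² and b = r^(8/3). With the past only, the residual variance is 1−a. With both sides it is (1−a)(1−b)/(1−ab). The proportional cut is 1 − (1−b)/(1−ab) = b(1−a)/(1−ab).
- r = 0.5: a = 0.25, b = 0.1575; cut = 0.1575 × 0.75 / 0.9606 = 12%
- r = 0.8: a = 0.64, b = 0.5515; cut = 0.5515 × 0.36 / 0.6470 = 31%

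If nothing is observed after Week 12, the cut is zero.

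**Effect on the treatment comparison.** A simulation compared earlier-visits-only FCS with all-visits FCS: 150 trials per setting, 40/40/40/20 subjects, 10 imputations, assumed SD 6 mm, equally spaced visits. It gives the mean Week 12 responder difference, Formulation 1 minus HV 2B:

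| Correlation | Missingness | Missing at Week 12 | Earlier only (SD) | All visits (SD) |
|---|---|---|---|---|
| AR(1) 0.7 | monotone | 11.0% | 0.078 (0.085) | 0.076 (0.085) |
| AR(1) 0.7 | intermittent | 9.9% | 0.076 (0.081) | 0.076 (0.081) |
| AR(1) 0.7 | early-termination value as Visit 8 | 11.0% | 0.082 (0.089) | 0.079 (0.087) |
| CS 0.5 | monotone | 11.1% | 0.067 (0.070) | 0.068 (0.070) |
| CS 0.5 | intermittent | 10.2% | 0.068 (0.073) | 0.068 (0.072) |
| CS 0.5 | early-termination value as Visit 8 | 11.2% | 0.066 (0.068) | 0.067 (0.067) |

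The largest change in the mean is 0.082 − 0.079 = 0.003, and in the SD 0.002. Neither model was consistently closer to the complete-data result.

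**The case against.** The strongest reply has four parts.

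- **The text is loose rather than contradicted.** SAP 4.2.9.1 says which variables are in the model, the variable list in 7.3.3 contains them all, and the wording can be read as chronological order. It never says that each visit is conditioned on every other. This stands: the two are not aligned, but a reader who infers a flat contradiction goes further than the text allows. Even so, 4.7.3 sends the reader to 4.2.9.1 for the FCS details, and those do not tell a programmer that later visits are excluded.
- **The listing is visibly faulty.** The missing Visit 6 line and the duplicates may be typing or PDF-reading errors. This stands too, so it cannot be said that every visit is predicted only from the past. It can be said of every printed line.
- **FCS for the responder is prespecified.** SAP 4.7.3 and the table titles in 7.1 say so, and LOCF and observed-data analyses are planned alongside. That is true, but it leaves unexplained why a method named only for sensitivity in 4.2.9.1 carries the main analysis. SAP 5 does not list the move away from MCMC.
- **Adding Visit 8 may import a mislabelled value.** Subjects who stop early are asked for Visit 8 assessments as soon as possible (Protocol 7.6.2, SAP 4.2.8), and SAP 4.2.10 analyses nominal visits. A Visit 8 record could predate Week 12, and the documents do not say how it is mapped. This is a sound caution. It applies equally to the MCMC primary analysis, so it calls for correct mapping and does not justify the restricted formulas.

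**Conclusion.** The point holds as one of specification. The printed FCS regressions ignore later visits, the Visit 6 model is absent, the Week 12 model is given twice, and this output feeds the main responder analysis while the continuous endpoint uses a joint model.

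The loss is about 1–3% (compound symmetry) to 12–31% (AR(1), 0.5–0.8 per 3 weeks) of the residual variance of a single imputed Week 12 value, and only where Visit 8 is observed. All the correlations are assumed. The simulated effect on the mean responder difference is 0.003 or less at 10–11% missing, also under assumed inputs.

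Stronger readings are tempting but not supported.

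- *The responder result is materially biased.* Nothing in the documents or the simulation shows this, and under monotone dropout nothing is lost.
- *The AR(1) loss is 20–39%.* That needs equally spaced visits; the actual gaps are 3 and 4 weeks.
- *The missing-at-random assumption is broken.* That is an assumption about the data; the code changes only what is conditioned on.
- *One value being a responder in one analysis and not in the other is itself a fault.* Random draws can differ in this way within one method. The issue is that the models differ.

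The primary continuous Schirmer analysis uses MCMC and is not affected.

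**What to change.** 1. Derive the Week 12 responder from the 25 MCMC-imputed datasets already used for the primary Schirmer analysis, and keep FCS as a sensitivity analysis. Point the code in 7.3.6 and 7.3.7 to the MCMC output, and change 4.7.3 and the titles of Tables 14.2.3.1.1 to 14.2.3.1.4 to match.
2. In 7.3.3 replace the restricted formulas with one statement in which all other listed variables predict each visit: `FCS NBITER=200 REG(AVAL2 AVAL4-AVAL9)`. This also restores a Visit 6 model and removes the duplicates.
3. State in 4.2.9.1 that each visit is imputed from treatment and all other visits, and define `AVAL9` in 7.3.1.
4. State that early-termination assessments made before Week 12 do not enter as `AVAL9` (Week 16) in either imputation model, and say how they are mapped.

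The cost is an edit to SAP text and code, best made before unmasking, plus correct visit mapping of the early-termination records. No new data are needed.
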